2 INTRODUCTION

2.1 STUDY RATIONALE

DISEASE BURDEN IN SEVERE ASTHMA AND THERAPY SELECTION

Asthma is a highly prevalent disease that affects 33 million people in the United States and Canada. The vast majority of asthma patients are well controlled with conventional asthma therapies; however, 10% of patients have severe disease that is associated with significant comorbidity and exposure to high doses of OCS. OCS use increases the odds of developing comorbid diseases such as diabetes, hypertension, cardiac disease and cataracts and is increasingly being recognized as a major contributor to severe asthma costs, making the development of alternative less harmful therapies paramount¹. Fortunately, over the past three years there has been a rapid increase in the number of biologics approved for the management of severe asthma with type II inflammation, which is estimated to be present in up to 60% of this population. The term type II inflammation refers to an increase in the levels of type II cytokines including IL4, IL5 and IL13, which induce pathologic downstream production of IgE and eosinophils. Current clinical practice utilizes surrogate biomarkers, including peripheral and sputum eosinophils, FeNO and total IgE levels, to phenotype patients with severe asthma and guide biologic drug selection. Unfortunately, these surrogates are imperfect and prone to error from multiple sources, especially in the obese².

Unequal Response to Therapy Despite Similar Biomarkers

The response to targeted biologic therapies is heterogeneous despite the use of well-studied biomarkers to select potential responders. Unfortunately, even when patients with a high likelihood of response are selected, 10-15% have complete non-response in all clinical parameters, and only 40% have a robust and complete response to therapy. This is likely related to the presence of overlapping inflammatory pathways, co-morbid eosinophilic diseases that affect response to therapy, possible sub-optimal dosing of drug and the lack of highly specific biomarkers. Precision medicine approaches to severe asthma are in their infancy and the application of complex techniques to help guide therapy are urgently needed. Currently, patients that are partial responders or non-responders to given therapies are switched between available biologics as a means of identifying the best therapy—an inefficient approach that is both time consuming and costly to patients and payers (**Figure 1**).

[figure not shown]

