
For the purposes of our analysis, we will define baseline measurements as the average of all data obtained in the year prior to biologic initiation or, if only one clinical encounter (defined as an office or emergency room visit) is available in this time period, then the average of the 2 clinical encounters immediately prior to biologic initiation will be used with the time frame noted in the database. In order to assess our primary and secondary outcomes we will use the average of all data from 4 to 18 months after biologic initiation or, if only one clinical encounter is available in this time period, the average of the 2 clinical encounters closest to, but not before 4 months after, biologic initiation. If a second biologic is introduced or the initial biologic choice is

changed, we will use all clinical data prior to the change, even if it is before 4 months of use, then follow the above steps to collect new outcome data on the new drug (see **Figure 4**).

[figure not shown]

Figure 4. Baseline and Response Clinical Data Plan.

Since our interest is primarily in finding the ~15% of patients who do not respond to biologics, we have chosen to include partial and complete responders together in our endpoints in order to isolate the non-responder population. Table 1 below will represent the dichotomization of responders and non-responders for each endpoint using the baseline and post-biologic data as detailed above. An exacerbation will be defined as any hospitalization, urgent care, emergency room, or unscheduled office visit for asthma or a breathing-related complaint or a temporary increase of OCS or ICS dosing for 3 or more days with the intent of the increase to treat acute symptoms. For clinician response, clinical encounter notes will be read and interpreted by 2 independent physicians and graded as detailed in the table. Upon completion of all data abstraction the patient will be de-identified as described in data handling below.

	Responder	Non-responder
Exacerbations	Any decrease from baseline	No change from baseline
Hospitalizations	Any decrease from baseline	No change from baseline
Maintenance oral corticosteroid (OCS) use	Any decrease from baseline	No change from baseline

Change in FEV1	$\geq 5\%$ improvement from baseline	<5% improvement from baseline
ACT score	≥ 1 -point improvement from baseline	No change from baseline
Clinician impression of response to therapy	Any improvement in symptoms from baseline	No change from baseline

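### The switch rule in 4.1 has no time limit, so patients who change biologic after month 4 are graded on a window that includes months 0–4, which can turn partial responders into non-responders

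*Combined protocol and SAP*

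**What the plan says.** All the relevant rules are in section 4.1, apart from one statement in 2.1.

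- **Baseline:** "the average of all data obtained in the year prior to biologic initiation".
- **Response, standard rule:** "we will use the average of all data from 4 to 18 months after biologic initiation".
- **Response, when only one encounter falls in that window:** "the average of the 2 clinical encounters closest to, but not before 4 months after, biologic initiation". This fallback keeps the month-4 start but has no month-18 cap.
- **Change of biologic:** the trigger is "If a second biologic is introduced or the initial biologic choice is" changed, and then "we will use all clinical data prior to the change, even if it is before 4 months of use". The steps restart for the new drug. The sentence neither limits the timing of the change nor restates the month-4 start or the month-18 cap. It refers to Figure 4, which was not available for this check.
- **Grading (Table 1):** for exacerbations, hospitalizations and maintenance OCS, a responder is "Any decrease from baseline". FEV1 needs an improvement of 5% or more, and ACT a gain of 1 point or more.
- **Aim:** partial responders are grouped with complete responders, to isolate the roughly 15% who do not respond.
- **Who switches (2.1):** "patients that are partial responders or non-responders to given therapies are switched between available biologics".

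Section 6 does not mention switching.

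**The concern.** The evident purpose of the switch sentence is to leave something gradeable when a patient changes drug before month 4. As worded, it also covers patients who change at month 8, 12 or 18 and already have data from month 4 onward. Two patients with the same course on the first drug would then be graded on different windows because one of them later switched.

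That later event is related to the outcome: section 2.1 says it is partial and non-responders who are switched. If months 0–4 show less benefit than later months, including them pulls a switcher's response toward baseline. The patients most exposed are partial responders, whom 4.1 wants in the responder class. The class they could be moved into is the small one the biomarkers are meant to identify.

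**Working it through.** The plan gives no figure of its own to reproduce, so this is a check of what the written rule does.

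**Inputs from the plan:** the windows and Table 1 thresholds above, and a 12-month baseline.

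**Assumptions, not in the plan:** data evenly spread over time; a stable effect from month 4; a fraction *f* of that effect present in months 0–4 (*f* = 0, 0.5 or 1); Poisson exacerbation counts.

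**1. Share of the window.** For a switch at month *s*, months 0–4 make up 4/*s* of the literal window: 4/6 = 67% at month 6, 4/8 = 50% at month 8, 4/12 = 33% at month 12 and 4/18 = 22% at month 18.

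**2. FEV1.** A gain *g* from month 4 averages *g*(4*f* + *s* − 4)/*s*. With *f* = 0, *g* = 6% and *s* = 12, this is 6% × 8/12 = 4.0%, a non-responder. On months 4–12 the same patient averages 6%, a responder. The gain needed to reach 5% is 5*s*/(4*f* + *s* − 4):

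| Switch at month | *f* = 0 | *f* = 0.5 | Window starting at month 4 |
|---|---|---|---|
| 9 | 9.0% | 6.4% | 5.0% |
| 12 | 7.5% | 6.0% | 5.0% |
| 18 | 6.4% | 5.6% | 5.0% |

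**3. ACT.** On Table 1's 1-point threshold, the gain needed at month 12 is 12/8 = 1.5 points with *f* = 0 and 12/10 = 1.2 points with *f* = 0.5.

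**4. Exacerbations, expected value.** With months 0–4 at the baseline rate and a rate ratio *r* afterwards, the expected ratio to baseline is [4 + *r*(*s* − 4)]/*s*. For *r* = 0.7 and *s* = 12 this is (4 + 5.6)/12 = 0.80, still a decrease. For any *r* below 1 it stays below 1, so dilution alone never brings the expected rate up to baseline. At *r* = 0.7 and *s* = 12, that would need a rate in months 0–4 of (12 − 8 × 0.7)/4 = 1.6 times baseline.

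**5. Exacerbations, observed label.** Counts are noisy, so the probability of a wrong label can still change. Let the baseline count be *B* ~ Poisson(3), given *B* ≥ 1. A patient is graded non-responder when the annualised later rate is not below *B*. For a true halving and a switch at month 8:

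- Months 4–8: mean count 3/12 × 4 × 0.5 = 0.5; misgraded 28%.
- Months 0–8, *f* = 0: mean count 3/12 × (4 + 4 × 0.5) = 1.5; misgraded 38%.
- Months 0–8, *f* = 0.5: mean count 3/12 × (4 × 0.75 + 4 × 0.5) = 1.25; misgraded 31%.
- Months 0–8, *f* = 1: mean count 3/12 × 8 × 0.5 = 1.0; misgraded 24%.

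As a control, a drug with no effect is graded non-responder 49% of the time on months 4–8 and 50% on months 0–8. The rise at *f* = 0 is therefore not mainly an effect of window length in this case. That does not hold for every switch time: with 2 per year, a halving and a month-12 switch, the figure goes from 23% to 39% at *f* = 0, but it is already 30% at *f* = 1, so part of that rise comes from window length and ties.

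**6. Maintenance OCS.** If the dose stays at baseline to month 4 and falls afterwards, the average over months 0–*s* is still below baseline. The label does not change.

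**The case against.** The strongest reply is that the sentence is a concession for early switches: stop at the change, and accept early data if nothing else exists. Figure 4 may say exactly that. This is a fair reading of the intent, but not of the words, and an abstractor following the words would build unequal windows. If Figure 4 limits the rule, the sentence should be made to match it.

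Second, the direction depends on delayed onset, which the plan does not state. This stands. With full effect from the start, the literal rule does slightly better at month 8 (24% against 28%), because more data are used.

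Third, more data per switcher has real value. For a switch at month 6, a window starting at month 4 is only 2 months long. At 3 per year, a drug with no effect would be graded non-responder 38% of the time, against 52% under the literal rule. This also stands, and the fix has to allow for it.

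A reader might go further in four ways that the documents do not support:

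- That late switchers are systematically moved into the non-responder class on the primary endpoint. Step 4 rules this out for the expected rate; only the misgrading probability changes.
- That OCS labels are affected. By dilution alone they are not (step 6).
- That data after month 18 push labels the same way. They have no fixed direction, and the sparse-data fallback can admit them for stayers too. This is a comparability point only.
- That a count of extra false non-responders can be given. The plan states neither how many patients switch nor when, and switchers include true non-responders, whose labels barely move at month 8.

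**Conclusion.** The point holds in a limited form. As written, the first-biologic response window for anyone switching after month 4 differs from that of patients who stay, and the difference is triggered by an event tied to poor response. Nothing in section 6 corrects this.

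The consequence is conditional on a weaker effect in months 0–4. Excluding those months for everyone else implies such a delay, but the plan does not say so. Given that delay, the shift is direct for the thresholds on FEV1 (secondary) and ACT (exploratory). For exacerbations (primary) it is a raised chance of misgrading: about 10 percentage points in the month-8 example with no early effect, about 3 with half the effect early, and reversed with full early effect. These figures rest on the assumed rates, effect sizes and switch times. The effect on the whole cohort cannot be estimated from the documents. The matter is worth settling before response labels are assigned.

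**What to change.** Check the sentence against Figure 4, then reword 4.1 along these lines: *If a biologic is added or changed at month s, after month 4, the response window for the first biologic runs from month 4 to the earlier of s and 18. Data before month 4 are used only when the change occurs before month 4, or when fewer than 2 encounters fall between month 4 and s. Such records are flagged.*

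Add two sensitivity analyses: one using all data before the change for every switcher, and one leaving out the flagged records. State also how use of data from before month 4 fits with the requirement in 5.2 for 4 or more months of follow-up.

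The cost is a sentence in 4.1, a date filter and a flag, because 4.1 already has all post-biologic data abstracted. The price is shorter and noisier windows for switches soon after month 4, as in the month-6 example. The 2-encounter safeguard limits this, and the first sensitivity analysis shows whether it matters.

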Secondary Objectives:	
1. To identify imaging biomarkers that are associated with the probability of any post-treatment improvement of FEV1 of 5% or more2. To identify imaging biomarkers that are associated with the probability of any post-treatment reduction in maintenance OCS use							
Exploratory Objectives:	
1. To identify imaging biomarkers that are associated with the probability of any reduction in pre-treatment baseline hospitalizations for asthma2. To identify imaging biomarkers that are associated with the probability of any post-treatment improvement in ACT score3. To identify imaging biomarkers that are associated with the probability of any subjective post-treatment reduction in symptoms described clinically							
Endpoints:	Primary Endpoint:	Determine the cutoff value in chest wall muscle size/quality that optimally classifies patients that had and did not have any reduction in pre-treatment baseline exacerbation frequency (binary). Alternative (continuous): determine the strength of the linear/non-linear relationship						

	between continuous chest wall muscle size/quality and continuous change in exacerbation frequency
Secondary Endpoints:	
 1. Determine individual and combinations of body composition measures (phenotypes) associated with a 5% or greater improvement in FEV1 when compared to baseline FEV1 2. Determine individual and combinations of body composition measures associated with any reduction in maintenance OCS use when compared to baseline OCS use
Exploratory Endpoints:	
These endpoints may be limited in scope of analysis by the sample size within each of the outcome groups.
 
 1. Determine individual and combinations of body composition measures associated with any reduction in hospitalizations when compared to baseline hospitalizations 2. Determine individual and combinations of body composition measures associated with any improvement in ACT score when compared to baseline ACT score 3. Determine individual and combinations of body composition measures associated with any subjective improvement of symptoms when compared to baseline symptoms

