3 OBJECTIVES AND ENDPOINTS

OBJECTIVES	ENDPOINTS	JUSTIFICATION FOR ENDPOINTS
Primary		
To identify imaging biomarkers that are associated with the probability of any reduction in pre-treatment baseline exacerbation frequency in a severe asthma population on biologics	Any reduction in exacerbations when compared to baseline exacerbations	Reduction in exacerbations is the primary clinical endpoint used in phase III trials to get many of the biologics used in asthma approved. Finding imaging biomarkers that associate with and possibly predict which patients will not have a reduction in exacerbations would be critical information for clinicians considering biologic initiation.
Secondary		
To identify imaging biomarkers that are associated with the probability of any post-treatment improvement of FEV1 of 5% or more	5% or greater improvement in FEV1 when compared to baseline FEV1	FEV1 is an important measure of lung function for patients with asthma, and any imaging biomarkers that predict a failure to improve this measure would be clinically useful.
To identify imaging biomarkers that are associated with the probability of any post-treatment reduction in maintenance OCS use	Any reduction in maintenance OCS use when compared to baseline OCS use	OCS are associated with multiple comorbidities, especially in the asthma population. Multiple phase III studies are currently underway to study maintenance OCS reduction in asthma due to this clinical concern and is a common reason for initiating biologics. Any imaging biomarkers that predict a failure to wean OCS after biologic initiation would be clinically useful.
Exploratory		
To identify imaging biomarkers that are associated with the probability of any reduction in pre-treatment baseline hospitalizations for asthma	Any reduction in hospitalizations when compared to baseline hospitalizations	Hospitalizations represent the most severe form of exacerbation and being able to find imaging biomarkers that associate with no improvement in hospitalizations would be clinically significant.
To identify imaging biomarkers that are associated with the probability of any post-treatment improvement in ACT score	Any improvement in ACT score when compared to baseline ACT score	Failure to improve symptoms after biologic initiation is a clinically frustrating scenario and finding imaging biomarkers that can predict this would be important for biologic initiation.

OBJECTIVES	ENDPOINTS	JUSTIFICATION FOR ENDPOINTS

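### No rule limits the OCS, hospitalization and exacerbation responder endpoints to patients with a non-zero baseline, so patients with nothing to reduce are graded non-responders

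*Combined protocol and SAP*

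**What the plan says.** Section 4.1 states that "Table 1 below will represent the dichotomization of responders and non-responders for each endpoint". Partial and complete responders are pooled "in order to isolate the non-responder population", which the same paragraph puts at about 15% of patients.

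For exacerbations, hospitalizations and maintenance OCS use, Table 1 makes any fall a response and "No change from baseline" a non-response. The ACT and clinician-impression rows use the same non-responder wording. Only the FEV1 row is exhaustive: its non-responder has "<5% improvement from baseline", which takes in any decline.

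Baseline is the average over the year before the biologic. If that year holds only one encounter, "the average of the 2 clinical encounters immediately prior to biologic initiation will be used".

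Sections 5.1 and 5.2 require an asthma diagnosis, an approved biologic and a chest CT, and exclude on smoking, emphysema, severe bronchiectasis from other causes, and inadequate follow-up. They do not require an earlier exacerbation, hospitalization or course of maintenance OCS. Sections 1.1, 3 and 6 add no such condition. Figure 4 (the baseline and response data plan) was not available in the text reviewed and could not be checked.

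**The concern.** A patient at zero before treatment cannot show a decrease. If that patient is also at zero afterwards, Table 1 grades a non-responder. This is not a failure of the biologic, yet the patient enters the small class that the imaging markers are meant to identify. For OCS it also sits badly with section 3, whose justification is to "predict a failure to wean OCS after biologic initiation": a patient who was never on maintenance OCS has nothing to wean.

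The elastic net, random forest and boosting models of section 6.3 would be trained on these labels. Calgary data graded by the same rules would not expose the problem. For OCS and hospitalizations, the model could end up mainly separating patients with a zero baseline from patients with a non-zero one.

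There is also a smaller wording matter. In five of six rows a patient who worsens has no class in Table 1. For ACT, the table asks for at least 1 point while section 3 accepts any gain. Because scores are averaged, a gain between 0 and 1 point is a response in one place and unclassed in the other.

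**Working it through.** The plan gives no event rates, no OCS prevalence and no sample-size calculation, so there is no figure to reproduce. From the documents: about 300 Michigan patients, about 15% non-response, a 12-month baseline window, and a response window of months 4 to 18 (14 months). Everything else below is assumed.

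**Maintenance OCS (secondary).** Let f be the share not on maintenance OCS at baseline and q the share of users who do not reduce. All non-users count as not decreased. Their share of labelled non-responders is c = f / (f + q(1 - f)).

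| f | Labelled non-responders of 300, q = 0.15 | c, q = 0.15 | c, q = 0.60 |
|---|---|---|---|
| 0.30 | 90 + 31.5 = 121.5 | 0.30/0.405 = 74% | 0.30/0.72 = 42% |
| 0.50 | 150 + 22.5 = 172.5 | 0.50/0.575 = 87% | 0.50/0.80 = 62.5% |
| 0.70 | 210 + 13.5 = 223.5 | 0.70/0.745 = 94% | 0.70/0.88 = 80% |

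At q = 0.15 the labelled class is 40.5% to 74.5% of the cohort, against the 15% that the study wants to isolate.

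**Hospitalizations (exploratory).** Let B and R be independent Poisson counts before and after treatment, with means r and r x 0.5 x 14/12 (rate halved). A non-responder has R >= B, compared on counts.

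| r per year | P(B = 0) | P(R >= B) | Zero-baseline share | P(0,0) | Zero-to-zero share |
|---|---|---|---|---|---|
| 0.1 | 0.905 | 0.910 | 99% | 0.854 | 94% |
| 0.5 | 0.607 | 0.686 | 88% | 0.453 | 66% |

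The shares are P(B = 0) and P(0,0), each divided by P(R >= B). Patients with B >= 1 number 300 x (1 - P(B = 0)), or about 28 and 118.

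**Exacerbations (primary).** The same model gives P(0,0) = exp(-r) x exp(-r x 0.5 x 14/12) = exp(-1.583 r). The last two columns divide this by the share of patients without a decrease: 0.553, 0.433, 0.368 and 0.323 on counts; 0.415, 0.260, 0.214 and 0.192 on rates.

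| r per year | Zero-to-zero, of all patients | Of labelled non-responders, counts | Of labelled non-responders, rates |
|---|---|---|---|
| 1 | 21% | 37% | 49% |
| 2 | 4.2% | 10% | 16% |
| 3 | 0.9% | 2% | 4% |
| 4 | 0.2% | 0.6% | 0.9% |

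**Worsening.** The texts can be set side by side. Table 1 is called a dichotomization; its FEV1 row is exhaustive; the synopsis splits the primary endpoint by whether or not there was any reduction; and section 3 speaks of patients who "possibly predict which patients will not have a reduction in exacerbations" might identify as not improving, and of failure to wean. All place a worsening patient with the non-responders. None suggests leaving such a patient out.

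**The case against.** **Worsening patients.** A reader might infer that these patients drop out of the analysis or that the primary endpoint is undefined. The documents do not support that: the other passages resolve the table's shorthand one way, and three of the five rows concerned are exploratory. This is a clarification, not a design error.

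**The primary endpoint.** A reader might also infer that it is swamped. Counting every zero-baseline patient at 2 per year gives 0.135/0.433 = 31% of labelled non-responders on counts and 0.135/0.260 = 52% on rates. Those figures include patients who went from zero to some exacerbations; they got worse on treatment, and calling them mislabelled is debatable. Low baseline rates are also weakly supported. The exacerbation definition is broad (any unscheduled breathing-related visit, or a steroid increase of 3 or more days), and section 4.2 says that CT is rare in stable asthmatics. At 4 per year on rates, the restriction moves the non-responder share only from 19% to 18%.

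**Loss of discrimination.** It is tempting to turn the shares into a loss of AUC. The model above cannot support that, because every patient's rate is halved and it therefore contains no true non-responders.

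**What the restriction achieves.** If instead 15% of patients are unaffected and 85% have their rate halved, at 2 per year on rates, 29% are labelled non-responders, 46% of them with a zero baseline. After the restriction 18% are labelled, and only about a third of these are the unaffected patients. The restriction removes patients who cannot respond; it does not by itself isolate the target class. This objection stands.

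**The synopsis caveat.** The synopsis warns that sample size may limit the exploratory endpoints. That bears on hospitalizations, but it is not a baseline rule and does not reach the secondary OCS endpoint.

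**Conclusion.** The missing denominator is real for all three endpoints, subject to Figure 4, which could not be checked. It matters most for maintenance OCS use, where non-users form 74-94% of labelled non-responders under the assumptions above and still 42-80% if 60% of users fail. It matters similarly for hospitalizations, at 88-99% zero-baseline on counts, or 66-94% if only zero-to-zero patients are counted. For the primary exacerbation endpoint it is modest at 2 or more per year and large only near 1 per year. Confidence is high for the text and low for any particular size.

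The point does not touch the FEV1 endpoint, the classification tree on SARP class or the clustering. The continuous alternative for the primary endpoint has no labels to get wrong, although the floor at zero remains. The worsening and ACT wording is a minor correction. The plan should fix these definitions before outcomes are graded, since a later choice could be steered by the results.

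**What to change.** 1. In section 4.1, restrict the OCS, hospitalization and exacerbation responder analyses to patients with a non-zero baseline on that endpoint, as measured by the existing baseline rule including its two-encounter fallback.
2. Report the number excluded for each endpoint, and repeat each analysis with all patients as a sensitivity analysis.
3. In the five Table 1 rows that read "No change from baseline", define the non-responder as no decrease or no improvement, with no change and worsening both included.
4. Reconcile the ACT row with the synopsis and section 3, so that averaged gains between 0 and 1 point are classed the same way throughout.

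No new data are needed: section 4.1 already abstracts OCS dosage and asthma encounters.

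The first cost is smaller analysis sets. For hospitalizations, about 28 to 118 of 300 patients remain at 0.1-0.5 per year. For OCS, 210, 150 or 90 remain if 30%, 50% or 70% are non-users. The second cost is some added regression to the mean. With no true effect at 2 exacerbations per year, dividing by P(B >= 1) = 0.865 raises the responder share from 34.0% to 39.4% on counts and from 52.3% to 60.5% on rates. This is why the all-patient analysis should be reported beside the restricted one.
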